4.6.3 Physical Examination

Physical examinations at screening will be summarized. Individual data on physical examinations will be listed.

4.6.4 Vital Signs

Vital signs (temperature, heart rate, weight, body mass index, and systolic and diastolic blood pressure) will be summarized descriptively by treatment sequence and visit time point (i.e., start of visit and end of visit) within each period. Change from the start of the visit will also be summarized by treatment group. Individual data on vital signs will be listed.

4.6.5 Electrocardiogram Findings

Electrocardiogram results will be summarized descriptively by treatment sequence and visit time point (i.e., start of visit and end of visit) within each period. Change from the start of the visit will also be summarized by treatment group. Individual data on electrocardiogram results, including Investigator's comments, will be listed.

4.6.6 Immunogenicity

Immunogenicity will be summarized descriptively by treatment sequence and visit time point along with the change from baseline to follow-up, where baseline is defined as the measurement from Visit 3 prior to IMP administration. Individual data will be listed.

4.6.7 Local Tolerability

Local tolerability and infusion site reactions will be summarized by treatment using frequency counts and percentages. Individual data, recorded with the Draize scale, regarding local tolerability and infusion site reactions will be listed.

4.6.8 Pain and Nausea

Pain and nausea will be summarized descriptively by treatment and visit time point (i.e., start of visit, hourly, and end of visit). Change from the start of the visit will also be summarized by treatment group. Individual data will be listed.

4.7 Secondary Endpoint Analyses

Secondary endpoint analyses will be performed on the Full Analysis Set. The same analysis will be repeated on the Per-Protocol Set, if it differs from the Full Analysis Set, to test the robustness of the analysis. All assessments will be presented by treatment group.

In general, descriptive statistics for the measurements (including percent change and/or change from baseline, if applicable) will be presented by treatment group and visit time point for all secondary endpoint variables to be analyzed. In cases where a treatment arm was not completed (and that arm was not repeated according to protocol criteria), available data from that arm will be used in the analysis.

4.7.1 Bionic Pancreas Function Endpoints

The plasma ZP4207/Lilly glucagon concentration will be summarized descriptively at each time point by treatment group (e.g. n, mean, SD, coefficient of variation [CV%], median, minimum, and maximum). Mean concentration will be plotted over time, by treatment group. Individual plasma concentration-time curves will be plotted by patient.

The analysis of BP function endpoints will be on an intention-to-treat basis. In cases where a treatment arm was not completed (and that arm was not repeated according to protocol criteria), available data from that arm will be used in the data analysis.

A paired t-test or the Wilcoxon signed rank test for comparison of means with normally or non-normally distributed residuals, respectively, will be used. The Shapiro-Wilk test will be used to determine the normality of the residuals for each comparison. The residuals will be obtained from an ANOVA model with treatment group as the fixed effect. If the p-value of the test is less than 0.001, the non-parametric method will be utilized to analyze the endpoint parameter. The sample SAS code for the paired t-test analysis involving the average percent of insulin dose amounts successfully delivered by the pump is included here:

```
.....  
Note: InsTrt1 = the average percent of insulin dose amount successfully  
delivered by the pump during treatment with Lilly glucagon.  
InsTrt2 = the average percent of insulin dose amount successfully  
delivered by the pump during treatment with ZP4207.  
.....  
proc ttest ;  
paired InsTrt1*InsTrt2;  
run;
```

In a secondary analysis, any period effect and any interaction between treatment and period will be looked for, although no such interaction is predicted for the efficacy outcomes. The efficacy outcomes will be analyzed using a mixed model including terms for treatment and period as fixed effects, an interaction term, and subject nested within sequence as a random effect. A patient must have a data value for both periods in order to be included in the analysis for the given parameter. The sample SAS code for this analysis is included here:

```
.....  
Note: Insulin = the average percent of insulin dose amounts successfully  
delivered by the pump  
subject = subject identification number.  
sequence = sequence order (1=glucagon/ZP4207, 2=ZP4207/glucagon).  
treatment = treatment group (1=Lilly glucagon, 2=ZP4207).  
period = analysis period number (1=Visit 3, 2=Visit 4).  
.....
```

```
.....  
proc mixed ;  
class subject sequence treatment period;  
model Insulin = treatment period treatment*period ;  
random subject(sequence);  
run;  
.....
```

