3. TRIAL OVERVIEW

3.1 Overall Trial Design and Treatment Assignment

[figure not shown]
This is a Phase 2 single-center, open-label, 2-part, randomized cross-over trial in adult patients (≥ 18 years of age) with T1DM. Patients who already manage their T1DM using continuous subcutaneous (SC) insulin infusion pump therapy will be enrolled. The trial will assess the safety and efficacy of the BP, using either the iLet or the iPhone platform, using the glucagon analog

ZP4207 versus Lilly glucagon. In Part 1, up to 10 patients will participate in two 1-day treatment arms in random order (iPhone-based BP using ZP4207 and iPhone-based BP using Lilly glucagon) according to the randomization scheme. In Part 2, up to 10 new patients will participate in two 1-day treatment arms in random order (iLet using ZP4207 and iLet using Lilly glucagon) according to the randomization scheme. The BP will also administer insulin (insulin lispro, Lilly Humalog) using the same blood glucose (BG) control algorithm for all 4 treatment arms. The trial will be conducted at the Massachusetts General Hospital (MGH) Diabetes Center in Boston, MA. Up to 40 patients will be enrolled in this trial with the expectation that up to 10 patients will complete each part of the trial.

[figure not shown]
The overall trial design is displayed in Figure 1.

Figure 1. Trial Design Schematic

Part 1:

Part 2:

Patients can only participate in 1 part of the trial.
 ADA = anti-drug antibodies, BP = bionic pancreas.

Patients who have completed the Screening Visit and meet all of the inclusion and none of the exclusion criteria will be enrolled. The order of the treatment visits will be randomized in blocks of 2 patients.

The schedule of events for the trial is provided in Table 1.

Table 1. SCHEDULE OF PROCEDURES – PARTS 1 AND 2

Trial Visit	Visit 1 [1] Screening	Visit 2 Training	Visit 3 [2] [3] [4] [5] (1 st Treatment Visit)	Visit 4 [2] [3] [5] (2 nd Treatment Visit)	Visit 5 ADA Assessment Visit [6]	Visit 6 Follow-Up [7]
Informed consent	X					
Assess/confirm eligibility	X	X				
Demographics	X					
Medical, surgical, and social history; allergies	X					
Concomitant illness	X					
Concomitant medications	X	X	X	X	X	X
Height, weight, physical examination, and vital signs including body temperature and blood pressure [8]	X		X [9]	X [9]		
12-lead ECG	X		X [10]	X [10]		
Urine HCG pregnancy test and menstrual history [11]	X		X	X		
FSH [12]	X					

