4. STATISTICAL METHODOLOGY

4.1 Baseline, Endpoint, and Other Statistical Considerations

The clinical statistical analyses will be performed by Medpace.

Descriptive summary statistics including number (n), mean, median, standard deviation (SD), and range (minimum, maximum) for continuous variables (interquartile range [25th, 75th percentile] for non-parametric tests), and counts and percentages for categorical variables will be used to summarize data, as appropriate. Where appropriate, p-values will be reported. All statistical tests will be conducted using 2-sided tests with 5% significance level and 95% confidence interval, unless otherwise stated.

For all analyses, the 2 treatment arms from Part 1 (iPhone-based BP) will be compared, and the 2 treatment arms from Part 2 (iLet) will be compared. The analyses of Part 1 will be completely separate from the analyses of Part 2.

All data will be listed in patient-level data listings.

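### The normality check that chooses between the paired t-test and the signed-rank test is run on treatment-only ANOVA residuals, not on the within-patient differences that the paired test depends on

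*SAP*

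**What the plan says.** SAP section 4.7.1 sets the rule in four steps.

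- Choice of test: "A paired t-test or the Wilcoxon signed rank test for comparison of means with normally or non-normally distributed residuals, respectively, will be used".
- Check: "The Shapiro-Wilk test will be used to determine the normality of the residuals for each comparison".
- Input to the check: "The residuals will be obtained from an ANOVA model with treatment group as the fixed effect".
- Threshold: "If the p-value of the test is less than 0.001, the non-parametric method will be utilized to analyze the endpoint parameter".

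The sample code for the comparison is a paired PROC TTEST ("paired InsTrt1*InsTrt2"). Section 4.1 sets the level of the comparison itself ("All statistical tests will be conducted using 2-sided tests with 5% significance level") and keeps the parts apart: "The analyses of Part 1 will be completely separate from the analyses of Part 2". Section 3.1 gives the size of Part 1, "up to 10 patients will participate in two 1-day treatment arms in random order", and plans up to 10 new patients for Part 2.

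Section 4.7.2 carries a similar analysis over to plasma glucose. No reason is given for the 0.001 cut-off.

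**The concern.** A paired t-test works on one number per patient, the difference between the two visits, and its small-sample validity rests on those differences being roughly normal. The residuals in section 4.7.1 are each arm's values minus that arm's mean. They contain the patient's own level, which the pairing removes, and they come as correlated pairs that Shapiro-Wilk treats as independent.

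The mixed model later in the same section has a random patient effect, so the SAP recognises the pairing in its analysis but not in its check. The strict cut-off then takes away most of the sensitivity that is left with about 10 pairs.

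At stake is which p-value is reported for each bionic pancreas function endpoint and for plasma glucose. Several function endpoints are percentages bounded at 100%, where non-normal data are plausible.

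**Working it through.** **Inputs from the SAP.** Shapiro-Wilk at p<0.001 on treatment-only residuals (4.7.1); comparison two-sided at 5% (4.1); about 10 pairs per part (3.1). Section 5 expects 20 to 24 randomized, so up to 24/2 = 12 per part if split evenly. The SAP states no error rate for the rule, so there is no figure to reproduce.

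**Assumptions.** The SAP gives no SDs or distributions. Let s be the patient effect and d the paired difference, independent and centred. Let r be the SD of s divided by the SD of d.

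**What the residuals carry.** If patient effects act equally on both arms, the two values are s − d/2 and s + d/2.

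- Variance of each, in units of Var(d): r² + 1/4. The between-patient share is 0.25/0.50 = 50% at r = 0.5, 1/1.25 = 80% at r = 1 and 4/4.25 = 94% at r = 2.
- Third moments: E(s³) − E(d³)/8 and E(s³) + E(d³)/8, with average E(s³). Skewness of d cancels in the pooled residuals, while skewness of s stays in full.
- If the skew enters one arm only, the values are s and s + d, and the average third moment is E(s³) + E(d³)/2. Skewness of d is then diluted but not lost.

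So the rule can miss skew that matters and react to skew that does not, and the size of each depends on how d arises.

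**Simulation.** 10 pairs, 4,000 trials per scenario; percent of trials that switch to the signed-rank test.

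| Scenario | r | SAP rule | Differences, 0.001 | Differences, 0.05 |
|---|---|---|---|---|
| Exponential d, normal s, equal on both arms | 0.5-2 | 0.2-0.9 | 7-9 | 43-44 |
| Log-normal d (log-SD 1), normal s, equal on both arms | 0.5-2 | 1.0-1.3 | 21-23 | about 60 |
| Normal d, log-normal s | 0.5 / 1 / 2 | 5 / 13 / 26 | 0.1-0.2 | about 5 |
| Normal d, log-normal s | 5 | about 42 | 0.1-0.2 | about 5 |
| Exponential d in one arm only | 0.25 | 20 | 8 | 44 |
| Exponential d in one arm only | 1-2 | 0.8-2 | 9 | 45-46 |

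In the third row, repeat runs reach 27% at r = 2. With independent normal errors at each visit, the rates are 2%, 8%, 21% and 39% at r = 0.5, 1, 2 and 5. With 8 or 12 pairs, exponential differences with equally shared patient effects give 0.2-1.0% under the SAP rule.

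**Percent-delivered type of endpoint.** Assume values near 99%, with failures of 10-40 points in one arm for 10-20% of patients. The SAP rule switches in 65-77% of trials when the between-patient SD is 0.5 points, 41-42% at 3 points and 1.5-2.2% at 10 points. Testing the differences at 0.001 gives 62-76% throughout. If instead 5-20% of patients have a large drop shared by both visits, so that the differences are normal, the SAP rule switches in 41-87% of trials, against at most 0.1% for the differences at 0.001.

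**Consequence for the comparison.** With skewed differences of mean zero, the 5% paired t-test has type I error of 9-10% (exponential) or 16% (log-normal). The signed-rank test does little better, at 8-10% and 14%. In one assumed setting with outlier-prone differences, the rule stayed on the t-test and had 40% power, against 48% for the signed-rank test.

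**The case against.** Several stronger readings are tempting and are not supported.

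- **That the rule hardly ever finds skewed differences.** A reader might infer this from the 0.2-0.9% row, but it depends on between-patient spread. With one-arm failures and little spread between patients, which is plausible for percent-delivered endpoints, the rule matches a 0.001 check on the differences. Nor is the tested quantity unrelated to the assumption: d is part of it.
- **That the wrong residuals account for the whole gap between about 1% and 44%.** That contrast mixes two cut-offs. Going from 0.05 to 0.001 on the differences takes 44% to about 8%; changing the residuals takes about 8% to under 1%.
- **That false switching above 40% is typical.** For log-normal patient effects it needs a between-patient SD about five times that of the differences.
- **That the reported p-values are badly inflated.** If the treatments do not differ and there is no period effect, paired differences are symmetric about zero even for skewed endpoints; type I error was then 3-5% for the t-test and for the rule. Moving normal differences to the signed-rank test leaves it valid (4.6-5.3%).
- **That the CGM time-in-range endpoints are affected.** Section 3.2.2.2 derives them from CGM data, while section 4.7.2 extends the analysis to plasma glucose. No text expressly places them under this rule.

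All of this stands and limits the size of the point. It does not rescue the check, which is still run on the wrong quantity at a cut-off that the SAP does not justify.

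**Conclusion.** The defect can be read from section 4.7.1 without any assumption: the check uses residuals without a patient term, while the selected test uses within-patient differences. Its size rests on assumed distributions and about 10 pairs.

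The rule often misses non-normal differences when patient effects act equally on both arms and the between-patient SD is about half that of the differences or larger. It can also switch without cause when patient effects are skewed. When patients differ little and the skew sits in one arm, it can perform as well as the same cut-off on the differences.

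The practical result is an ill-chosen test and some loss of power under outliers. Only secondary endpoints are affected, and the primary safety comparison is qualitative (section 4.6). It is worth correcting because the correction is cheap, not because a main conclusion is at risk.

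**What to change.** In section 4.7.1, name one paired method in advance for each endpoint and drop the pre-test. If a check is kept, apply Shapiro-Wilk to the within-patient differences at a conventional level such as 0.05. This is the weaker option, since with 10 pairs it finds exponential skew only about 44% of the time.

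Report the other test as a sensitivity analysis. State that the signed-rank test assumes symmetric differences and does not compare means, which the present sentence on the two tests blurs. Say in section 4.7.2 whether the CGM-derived endpoints follow the same method.

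The cost is a paragraph of SAP text and minor code, with no change to trial conduct. It should be settled before any database lock, including the possible interim lock after Part 1 (section 4.7.4). The downsides are slightly lower power of the rank test where differences are in fact normal, and a different estimand wherever it is used.

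### Secondary endpoints: the main cross-over test has no period term, and the both-periods rule does not fit the stated intention-to-treat basis

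*SAP*

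**What the plan says.** SAP section 3.1 gives the design: "This is a Phase 2 single-center, open-label, 2-part, randomized cross-over trial in adult patients". Treatment order is randomised in blocks of two. Under section 4.1, "The analyses of Part 1 will be completely separate from the analyses of Part 2", and section 3.1 plans "with the expectation that up to 10 patients will complete each part of the trial", so each comparison rests on about ten patients.

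Section 4.7.1 tests the treatment difference with a paired t-test. If the Shapiro-Wilk p-value is below 0.001, it uses the Wilcoxon signed rank test instead. The sample code pairs the two treatment values within patient and contains no period. Period enters only afterwards: "In a secondary analysis, any period effect and any interaction between treatment and period will be looked for". That analysis is a mixed model, coded as "model Insulin = treatment period treatment*period" with a random patient effect nested in sequence, and its entry rule is "A patient must have a data value for both periods in order to be included in the analysis for the given parameter". Section 4.7.2 applies a similar analysis to the plasma glucose measurements.

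On the population, section 4.7 says "Secondary endpoint analyses will be performed on the Full Analysis Set" and section 4.7.1 says "The analysis of BP function endpoints will be on an intention-to-treat basis". Section 4.2 defines the Full Analysis Set, which it equates with the intention-to-treat population, as everyone randomised, with exceptional, documented exclusions.

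**The concern.** In an AB/BA design the within-patient treatment difference contains the period shift with one sign in one sequence and the opposite sign in the other. A paired test pools these differences as if they had a common mean. The shift then inflates the variance and, if the sequences are unequal in size, no longer cancels from the estimate. Including period removes both problems, and the SAP already specifies a model that does so, but ranks it second.

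The population wording is a separate matter. A randomised patient with a value in one period only belongs to the named analysis set but enters neither the paired test nor the mixed model. No comparative analysis in section 4.7.1 therefore covers the population that the SAP says it covers.

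At stake are the width of the intervals and the clarity of the estimates for the tested secondary endpoints, with about ten patients per part.

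**Working it through.** **Inputs.** From the SAP: two sequences, blocks of two, up to 10 completers per part, 20 to 24 randomised in total (section 5), two-sided 5% tests. An equal split of 24 gives 12 per part. The SAP gives no SD, treatment effect, period effect or within-patient correlation, and no formal sample size calculation, so there is no figure to reproduce. Assumed: SD of the within-patient difference = 1, period effect k from 0 to 1 in those units, correlation 0 to 0.9, and a treatment effect of 1 SD for power.

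**1. Interval width, 5+5 patients.** The within-patient differences have mean τ + k in one sequence and τ − k in the other, where τ is the treatment effect. The paired test's variance estimate then has expectation 1 + k² × 10/9 on 9 degrees of freedom. The period-adjusted analysis has variance 1 on 8. The ratio of interval widths is

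t(9) × √(1 + k² × 10/9) / t(8), with t(9) = 2.262 and t(8) = 2.306.

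| Period effect k | Width, paired / adjusted | Power, paired | Power, adjusted | Type I error, paired |
|---|---|---|---|---|
| 0 | 0.981 | 80% | 79% | about 5% |
| 0.25 | 1.014 | – | – | – |
| 0.5 | 1.109 | 72% | 79% | 3.1% |
| 0.75 | 1.251 | 62% | about 79% | – |
| 1 | 1.425 | 48% | 79% | 0.7% |

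Power and type I error come from simulation (200,000 trials per scenario; 40,000 for k = 0.75). The simulated mean half-widths agree closely with the formula: 0.695 against 0.706 at k = 0, 0.788 against 0.707 at 0.5, and 1.019 against 0.707 at 1.

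The break-even point solves 1 + k² × 10/9 = (2.306/2.262)² ≈ 1.039, so k ≈ 0.19. Below that, the paired interval is the narrower one.

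**2. Bias.** The paired estimate is biased by k × (n1 − n2)/(n1 + n2), where n1 and n2 are the analysed patients per sequence. This is zero at 5+5 or 6+6, 0.11k at 5+4, 0.20k at 6+4 and 0.25k at 5+3. The adjusted estimate was unbiased in all of these. The paired test's type I error did not exceed about 5% in any scenario.

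**3. Both-periods rule.** Take 12 randomised and 10 complete, with two patients having period 1 only. The quantity is the reduction in the variance of the treatment estimate if those two are kept, without an interaction term.

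| Correlation | 6+4 complete, both single-period patients in the smaller sequence | 5+5 complete, one in each sequence |
|---|---|---|
| 0 | 11.1% | 9.1% |
| 0.5 | 5.9% | 4.8% |
| 0.9 | 1.2% | 1.0% |

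Hand check at correlation 0, 6+4: the information is 1/(1/6 + 1/6) = 3 from period 1 and 1/(1/6 + 1/4) = 2.4 from period 2, total 5.4. Completers alone give 2.4 + 2.4 = 4.8. The reduction is 1 − 4.8/5.4 = 11.1%.

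**4. The treatment-by-period term.** Code treatment and period as ±1. Their product is +1 at both visits in one sequence and −1 at both visits in the other, so it is the sequence contrast. With complete data, generalised least squares with and without this term gave the same averaged treatment estimate and variance at 5+5, 6+4 and 5+3.

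**The case against.** The best reply is that the period-adjusted model is already planned, with code, and will be run whatever the paired test shows. No testing hierarchy or sample size depends on which analysis comes first. That stands: the issue is the order of two specified analyses. It still matters which one supplies the headline estimate, because the SAP does not say which result stands if they differ.

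A reader might infer that the paired test always loses precision. It does not. Below a period effect of about 0.19 SD its interval is the narrower, and at 0.25 SD it is only 1.4% wider. The visits are standardised and at most three weeks apart, and nothing in the SAP shows that an effect of 0.5 to 1 SD is likely.

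A reader might also infer that the estimate is biased. Bias needs a period effect and unequal sequences together. Blocks of two keep allocation close to equal, so imbalance would come mainly from dropout. The both-periods rule creates no period bias in a model that adjusts for period.

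The promise to use available data from an uncompleted arm can be kept whenever a partial arm yields a value. The conflict is therefore confined to patients with no value at all in one period, and they still appear in the descriptive summaries.

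Finally, the interaction term might be read as an error. The SAP says only that an interaction will be sought and is not predicted. It does not claim to separate interaction from carry-over or from a sequence difference, so the equivalence in step 4 is a note on interpretation.

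**Conclusion.** The point holds in a limited form. For the secondary endpoints tested under section 4.7.1, and by extension section 4.7.2, the main comparison leaves out a design factor that the SAP's own second model includes. The cost is conditional: an interval about 11% wider at a period effect of 0.5 SD and 43% wider at 1 SD, against about 2% narrower with none, for 5+5 patients. The error is towards conservatism when sequences are balanced, and bias appears only with imbalance as well.

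The population conflict holds as a matter of text: patients with a value in one period only are in the named set but outside both comparative analyses. Its precision cost is small, about 1–11% of variance in the case of 12 randomised and 10 complete.

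All sizes rest on assumed period effects and correlations. A reader might take this as a weakness in the trial's primary conclusion. The SAP does not support that: the primary safety endpoints are summarised descriptively and compared qualitatively, and are unaffected.

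**What to change.** - Name the mixed model with treatment and period as fixed effects and patient as random effect as the main analysis for sections 4.7.1 and 4.7.2. Report the treatment difference with its 95% confidence interval; the sample code needs a statement that requests it.
- Delete the both-periods rule so that every patient with data from at least one period enters. Otherwise keep the rule, call the comparison a completer analysis and remove the intention-to-treat wording from it.
- Keep the paired t-test as a sensitivity check. It remains a completers-only analysis and should be labelled so.
- When the rank method is triggered, compare within-patient period differences between the two sequences in place of the signed rank test.
- If the treatment-by-period term is kept, state that it equals the sequence contrast, a comparison between patients of about 5 against 5.

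The cost is SAP wording and minor code edits, plus one error degree of freedom: an interval about 2% wider, and about one percentage point of power, if there is no period effect.
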